### 10.3 Analysis Populations

All patients receiving at least one dose of BBI608 will be considered evaluable for safety analysis. Adverse event incidence rates will be described by the frequency of adverse events, categorized by NCI CTCAE. Listings of laboratory test results collected at baseline and during the study will be generated. Descriptive statistics summarizing the changes in those laboratory tests over time will be presented.

Patients who have received at least one cycle of study treatment and have had at least one disease assessment following the initiation of therapy will be considered evaluable for disease control rate and overall response. Progression-free survival and overall survival will be evaluated in the intent-to-treat population. Anti-tumor activity will be evaluated on an exploratory basis and will be summarized using descriptive statistics or graphics.

### 10.4 Efficacy

The primary population for the efficacy evaluation will be the evaluable population, defined as patients who have been treated with at least 80 % of 1 complete cycle of BBI608 and a combination drug. The primary efficacy outcome measure will be disease control rate, defined as the proportion of patients with a documented complete response, partial response and stable disease (CR + PR + SD) based on RECIST. In addition, progression-free survival (PFS) and overall survival (OS) will be obtained from intent-to-treat patients. PFS will be calculated from the date of patient enrolment into the trial until documented disease progression based on RECIST. OS will be calculated from the date of patient enrolment into the trial until death.

### 10.5 Demographics and Baseline Characteristics

Patient characteristics will include a complete summary of the following and will be recorded in the CRFs:

- Patient demographics
- Baseline disease characteristics
- Pre-existing conditions
- Prior therapies
- Concomitant medications and treatments

Other patient characteristics will be summarized as appropriate

### 10.6 Statistical Analysis of Pharmacokinetic Variables

Pharmacokinetics will only be performed on the first 6 patients enrolled in each combination arm of this study.

Timed blood sample collection for BBI608 and Cetuximab pharmacokinetic analysis will be performed on Days 5-11 and 26-32 after the first dose of Cycle 1 for the first 6 patients enrolled in the Cetuximab arm. Timed blood sample collection for BBI608 and Panitumumab pharmacokinetic analysis will be performed on Days 8-14 and 22-28 after the first dose of Cycle 1 for the first 6 patients enrolled in the Panitumumab arm. Timed blood sample collection for BBI608 and Capecitabine pharmacokinetic analysis will be performed on Days 8-9 and 21-22 after the first dose of Cycle 1 for the first 6 patients enrolled in the Capecitabine arm.

Bioanalytical analysis of patient samples will be conducted at a centralized laboratory using GLP-validated assays. Plasma concentrations will be summarized by descriptive statistics, including mean, standard deviation, coefficient of variation, minimum, maximum, and median.

Concentration profiles will be analyzed by noncompartmental and/or nonlinear least squares regression using WinNonLin. Pharmacokinetic parameters, including  $C_{max}$ , volume of distribution, distribution half-life, terminal half-life, and AUC will be evaluated.

### 10.7 Safety Analysis

Safety will be assessed by physical examination, and laboratory assessments. Adverse events will be graded according to the NCI CTCAE, version 4.0. The incidence of adverse events and DLTs will be evaluated for each combination arm, and for all patients combined. Patients will be followed for adverse events for at least 30 days after the last dose of BBI608, or until recovered from all related BBI608 adverse events.

### 10.8 Analysis and Sample size for sub-cohorts

Each sub-cohort will be analyzed for number of days of Grade II/III diarrhea and % treatment compliance achieved during the first two cycles. The % treatment compliance will be calculated as the number of capsules actually ingested over the number of capsules that should have been ingested per dose level multiplied by 100. The research questions addressed by sub-cohorts are hypothesis-generating and exploratory in nature. Initially 6 subjects will be assigned to each sub-cohort to assess the effect of intervention. Selected sub-cohorts will be extended to enroll up additional 20 patients. The decision of extending the enrollment will be based on clinical assessment without formal statistical testing. However, 20 patients will give 80% power to detect 20% difference in % treatment compliance between two arms and 57% power to detect the difference of 25% in the number of days of having Grade II/III diarrhea using two-sided Z test with pooled variance at type I error rate of 0.15. The control rates assumed are 70% for treatment compliance and 30% for diarrhea. The patients will be sequentially allocated to different sub-cohorts by the Sponsor to avoid section bias.

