Each sub-cohort will be analyzed for number of days of Grade II/III diarrhea and % treatment compliance achieved during the first two cycles. The % treatment compliance will be calculated as the number of capsules actually ingested over the number of capsules that should have been ingested per dose level multiplied by 100. The research questions addressed by sub-cohorts are hypothesisgenerating and exploratory in nature. Initially 6 subjects will be assigned to each sub-cohort to assess the effect of intervention. Selected sub-cohorts will be extended to enroll up additional 20 patients. The decision of extending the enrollment will be based on clinical assessment without formal statistical testing. However, 20 patients will give 80% power to detect 20% difference in % treatment compliance between two arms and 57% power to detect the difference of 25% in the number of days of having Grade II/III diarrhea using two-sided Z test with pooled variance at type I error rate of 0.15. The control rates assumed are 70% for treatment compliance and 30% for diarrhea. The patients will be sequentially allocated to different sub-cohorts by the Sponsor to avoid section bias.

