## 7.3 Treatment Compliance

A patient is considered compliant with the study protocol when study medication is administered at a compliance level of greater than 80%.

BBI608 compliance will be calculated using the following equation:

(Number of capsules actually ingested /number of capsules that should have been ingested per dose level) x 100= % compliance

Capecitabine compliance will be calculated using the following equation:

(Number of capsules actually ingested /number of capsules that should have been ingested per dose level) x 100=% compliance

Cetuximab or Panitumumab compliance will be calculated using the following equation:

(Number of treatments performed /number of treatments that should have been performed per dose level) x 100=% compliance

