4. HYPOTHESES AND DECISION RULES

4.1. Statistical Hypotheses

There is no hypothesis testing in this study.

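### The 80% power stated for sub-cohort compliance does not follow from the protocol's own inputs: 20 per group gives about 56% for 70% versus 90%

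*Protocol*

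**What the plan says.** Protocol 10.8, repeated in the synopsis under Statistical Methods, analyses each sub-cohort for "number of days of Grade II/III diarrhea and % treatment compliance achieved during the first two cycles". Compliance is defined per patient, as capsules taken over capsules due, times 100. Each sub-cohort starts with 6 patients, and selected ones may be extended by up to 20.

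The power statement for the extension is "20 patients will give 80% power to detect 20% difference in % treatment compliance between two arms and 57% power" to detect a 25% difference in diarrhea days, "using two-sided Z test with pooled variance at type I error rate of 0.15". It adds: "The control rates assumed are 70% for treatment compliance and 30% for diarrhea".

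The same section calls the sub-cohort questions exploratory and says "The decision of extending the enrollment will be based on clinical assessment without formal statistical testing". SAP 4.1 says "There is no hypothesis testing in this study", and the SAP gives no sub-cohort power.

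**The concern.** The statement gives enough inputs to be recomputed: test, sidedness, alpha, control rate, difference and a patient number. At 20 per group, an 80% chance of detecting a 20-point change from 70% looks too high, even at alpha 0.15.

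The sentence also leaves out what a reader needs in order to interpret either figure:

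- which two groups are compared;
- whether 20 is per group, in total, or on top of the first 6;
- the direction of each difference;
- the scale. The endpoints are a per-patient percentage and a count of days, but the calculation uses control rates, as for proportions of patients. Section 7.3 does define a compliant patient (above 80%), but 10.8 does not refer to it.

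At stake is how the extension can be read. Tolerability by starting dose and by anti-diarrheal strategy is a secondary objective (Protocol 2.2), and these two figures are the only quantitative support offered for extending by 20. If the true power is near 56%, a real 20-point gain would be missed about 44% of the time rather than 20%.

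**Working it through.** **Inputs (Protocol 10.8):** two-sided alpha 0.15, so z = 1.4395; pooled variance under the null; control rates 70% (compliance) and 30% (diarrhea); differences of 20 and 25 points; 20 patients. Equal allocation, 20 per group and absolute differences are assumed unless stated otherwise.

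**Formula.** For rates p1 and p2 with mean p̄, difference d = |p1 − p2| and n per group:

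- SE0 = √(2·p̄(1 − p̄)/n)
- SE1 = √((p1(1 − p1) + p2(1 − p2))/n)
- Power = Φ((d − z·SE0)/SE1) + Φ((−d − z·SE0)/SE1)

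**Step 1: the stated 80%.** For 70% versus 90%, n = 20:

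- SE0 = √(2 × 0.8 × 0.2/20) = 0.1265, so z·SE0 = 0.1821
- SE1 = √((0.21 + 0.09)/20) = 0.1225
- Upper tail Φ((0.20 − 0.1821)/0.1225) = 0.5581; lower tail 0.0009
- Power = **55.9%**. Exact binomial enumeration of the same test gives 58.1%.

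The 80% is not reproduced.

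**Step 2: the stated 57%.** For 30% versus 55%, n = 20: SE0 = √(2 × 0.425 × 0.575/20) = 0.1563, SE1 = √((0.21 + 0.2475)/20) = 0.1512, power = **56.6%**. This matches. The other direction, 30% versus 5%, gives 75.1%. So the two-proportion, 20-per-group reading recovers one stated figure and misses the other by about 24 points.

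**Step 3: other group sizes and directions, same test.**

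| Comparison | n per group | Power |
|---|---|---|
| 70% vs 90% | 10 (20 in total) | 37.4% |
| 70% vs 90% | 20 | 55.9% |
| 70% vs 90% | 26 (6 + 20) | 64.7% |
| 70% vs 90% | 40 | 79.5% (80.2% exact) |
| 70% vs 90% | 41 | 80.3% |
| 70% vs 50% | 20 | 44.2% |
| 70% vs 50% | 62 | 80.3% |
| 30% vs 55% | 20 | 56.6% |
| 30% vs 55% | 40 | 80.2% |
| 30% vs 5% | 12 | 57.3% |
| 30% vs 5% | 20 | 75.1% |

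The compliance figure of 80% needs about 40 per group (for a rise) or 62 (for a fall). The diarrhea figure of 57% needs 20 (for a rise) or 12 (for a fall). No single equal group size gives both. With 20 per group, 80% power for compliance needs a gain of about 26.3 points (70% versus 96.3%).

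**Step 4: compliance as a continuous per-patient percentage.** Power is then Φ(20/(SD·√(2/20)) − z) plus a negligible second tail. It depends on an SD that the documents do not give, so a range is shown for n = 20 per group:

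| Assumed SD (points) | Power for a 20-point difference |
|---|---|
| 20 | 96% |
| 27.7 | 80% |
| 30 | 75% |
| 40 | 56% |

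**The case against.** There are two serious alternative readings, and a point about weight.

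*Compliance is continuous.* Section 10.8 does define it per patient, and a Z test with pooled variance can also compare means. With an SD near 28 points, 80% at 20 per group would be correct. This cannot be excluded. But no SD is stated, and a control mean has no role in a two-mean power calculation, whereas control rates of 70% and 30% are exactly what a two-proportion calculation needs. The match on the 57% points the same way. If means were intended, the statement lacks its main input.

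*The comparison is pooled.* Protocol 2.2 names two contrasts: 240 mg versus 480 mg starting dose, and prophylactic versus as-needed anti-diarrheal treatment. With 20 in each of the four sub-cohorts, each contrast is 40 versus 40, which gives 79.5%. Because sub-cohorts exist within each combination arm, pooling two selected sub-cohorts across two arms would also give 40 versus 40. This may be where the 80% came from. However, 10.8 does not link its 20 patients to either contrast, extends only selected sub-cohorts, and would then be quoting the 57% on a different group size in the same sentence.

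*Little depends on it.* This stands. Extension rests on clinical assessment, SAP 4.3 bases sample size on clinical considerations, and the primary disease control analysis is untouched.

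**Conclusion.** The 80% is not supported by the inputs stated beside it. As two proportions with 20 per group, under the protocol's own test, power is 55.9% for 70% versus 90%, about 24 points lower than stated, and 44.2% for 70% versus 50%. This rests on 1:1 allocation, an absolute 20-point difference and compliance read as a proportion of patients. The 80% can be recovered with about 40 per group, or with a continuous endpoint and an SD of about 27.7 points, but the protocol states neither. The 57% for diarrhea is not shown to be wrong: it fits 30% versus 55% at 20 per group, although the text does not confirm that direction. The statement should be corrected. The effect is confined to it, because the sub-cohort questions are exploratory and no test or decision uses the figure.

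**What to change.** In Protocol 10.8 and the synopsis, do one of the following for compliance:

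- replace the 80% with about 56% power for 70% versus 90% with 20 per group; or
- keep 80% and say what it applies to: a pooled comparison of about 40 versus 40, naming the groups, or a gain of about 26 points with 20 per group.

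For both figures, state the two groups compared, the number per group (and whether it includes the first 6) and the direction. For the 57%, 30% versus 55% at 20 per group is the case that reproduces; the sponsor should confirm that this was intended.

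State the scale. If the 70% and 30% are proportions of patients, define the event, for example by reference to the compliance threshold in 7.3. If they are means of the endpoints as 10.8 defines them, give the assumed SDs and recompute.

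The cost is wording in two places. One figure becomes less favourable or is tied to a named comparison. No patients are added and no endpoint changes.

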## 2.2 Secondary Objectives

The secondary objectives of the study are:

- To determine the pharmacokinetic profile of BBI608 and Cetuximab, or Panitumumab, or Capecitabine when administered in combination.
- To determine the pharmacodynamics (biomarkers) of BBI608.
- To evaluate tolerability of two dosing regimens of BBI608 by comparing administration of BBI608 at 240 mg twice daily starting dose and escalating to 480 mg twice daily after cycle 1 versus administration of BBI608 at 480 mg twice daily starting dose with dose adjustment permitted.
- To evaluate tolerability of BBI608 by comparing prophylactic administration of anti-diarrheal medication versus as needed administration of anti-diarrheal medication. The tolerability will be assessed using adverse event profile and achieved dose intensity.

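### The 57% power quoted for days of diarrhea is a two-proportion power that matches 30% v 55%; a fall from 30% to 5% would have about 75%, and neither figure applies to a day count

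*Protocol*

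**What the plan says.** Protocol 10.8 analyses each sub-cohort for days of Grade II/III diarrhea and for percentage treatment compliance over the first two cycles. It starts with six patients per sub-cohort ("Initially 6 subjects will be assigned to each sub-cohort to assess the effect of intervention") and allows selected sub-cohorts to be extended by up to 20.

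It then offers two power figures. The first is for compliance: "20 patients will give 80% power to detect 20% difference in % treatment compliance between two arms". The second, for diarrhea, is "57% power to detect the difference of 25% in the number of days of having Grade II/III diarrhea using two-sided Z test", and both are obtained "using two-sided Z test with pooled variance at type I error rate of 0.15". The rates behind them are given in one sentence: "The control rates assumed are 70% for treatment compliance and 30% for diarrhea". The synopsis repeats all of this.

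The comparisons served are in Protocol 2.2: a 240 mg v a 480 mg twice-daily start, and "comparing prophylactic administration of anti-diarrheal medication versus as needed administration of anti-diarrheal medication". Section 10.8 calls the sub-cohort questions exploratory and leaves extension to clinical judgement without a formal test.

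The SAP gives no sub-cohort power. Under Adverse Events (8.2.4.1) it summarises the number of days of diarrhea of Grade II or above.

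**The concern.** A power figure is useful only if the reader can tell which effect it refers to. Here one rate is given (30%), the difference of 25% has no sign, and no sub-cohort is named as control. Prophylactic anti-diarrheal treatment and a halved starting dose would ordinarily be expected to reduce diarrhea, so most readers will take the target to be a fall from 30% to 5%. The quoted 57% does not belong to that effect.

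The second difficulty does not depend on direction. The power is claimed for a number of days. A Z test with pooled variance and a control rate in percent is a comparison of two proportions. Power for a count of days needs an expected mean and a spread, and neither document gives them.

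At stake is whether the figure offered in support of 20 patients describes the tolerability comparison that will be made. No primary conclusion depends on it.

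**Working it through.** **Inputs**
- Test: two-sided Z test, pooled variance, alpha 0.15 (Protocol 10.8), so z = 1.4395.
- Control rate for diarrhea: 30% (Protocol 10.8).
- Difference: 25%, read as 25 percentage points; direction not stated.
- Group size: the text says 20 patients. Taken as n = 20 in each of two equal groups; this is an assumption, tested below.

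**Formula**

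With p̄ = (p1 + p2)/2,

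se0 = √[2 p̄(1 − p̄)/n], se1 = √{[p1(1 − p1) + p2(1 − p2)]/n},

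power = Φ[(|p1 − p2| − z·se0)/se1].

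**The plan's figure: 30% v 55%**
- p̄ = 0.425; se0 = √(2 × 0.425 × 0.575/20) = 0.1563; z·se0 = 0.2250
- se1 = √[(0.21 + 0.2475)/20] = 0.1512
- (0.25 − 0.2250)/0.1512 = 0.165; power = **56.6%**

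This reproduces the stated 57%. The exact rejection probability of the same test, by enumerating all outcomes, is 57.5%. The formula is symmetric, so it does not matter which of the two groups has 30%.

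**The same inputs for a fall: 30% v 5%**
- p̄ = 0.175; se0 = √(2 × 0.175 × 0.825/20) = 0.1202; z·se0 = 0.1730
- se1 = √[(0.21 + 0.0475)/20] = 0.1135
- (0.25 − 0.1730)/0.1135 = 0.679; power = **75.1%** (exact 77.9%)

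The gap from the stated figure is 75.1 − 57 = 18 points. The two results differ because the binomial variance is larger near 50% than near zero.

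**Could another version of the test give 57% for the fall at 20 per group?** None of those tried does.

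| Version, 30% v 5%, 20 per group | Power |
|---|---|
| Unpooled variance | 77.7% |
| Pooled standard error throughout | 73.9% |
| One-sided | 86.6% |
| Continuity-corrected | 59.4% |
| Fisher's exact test | 62.2% |

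**Sensitivity to group size**

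| n per group | 30% v 55% | 30% v 5% |
|---|---|---|
| 10 (20 in total) | 37.5% | 51.3% |
| 20 | 56.6% | 75.1% |
| 26 (6 + 20) | 65.4% | 83.8% |

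Of these, only 20 per group with 30% v 55% gives 57%. For the fall, the formula comes close to 57% only at sizes that the text does not give for this comparison: about 12 per group (57.2%), or 6 control patients against 20 (58.7%).

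**A relative 25% fall** (30% to 22.5%) has 18.3% power, or 20.7% counting both tails, so the figure was not derived on a relative scale.

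**The unit.** All of these results are for proportions. For a mean number of days the corresponding calculation needs the difference in mean days and its SD. Neither document supplies either, so no power for the day count can be reproduced or corrected.

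**The case against.** The best defence is that there is no arithmetic error: 57% follows from the stated inputs. That stands. The faults are the missing direction and control group, and the unit.

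A reader might go further and infer that the sponsor powered the comparison for harm, with the test regimen nearly doubling diarrhea. The documents do not support this. The test is two-sided, Protocol 2.2 only speaks of comparing regimens, and no sub-cohort is called control. If 30% were the rate under prophylaxis or the lower start and 55% the rate in the comparator, the same 57% would describe a benefit. That is a less natural use of the term control rate, but the text does not exclude it.

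A reader might also infer that those deciding on extension are misled. Section 10.8 bases that decision on clinical assessment without formal testing. Protocol 10.1 plans no formal analysis, SAP 4.1 has no hypothesis testing, and SAP 4.3 rests the sample size on clinical considerations. No rule uses the 57%. If a fall is meant, the figure is also conservative.

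It is fair to add that the companion compliance figure is in a worse state: at 20 per group, 70% v 90% gives 55.8% and 70% v 50% gives 44.0%, against the stated 80%. That is a separate matter and does not repair the diarrhea figure.

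What the defence does not answer is the unit. A two-proportion power is attached to a day count whichever direction is meant.

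**Conclusion.** The point holds in a limited form. The stated 57% is a valid two-proportion power for 30% v 55% with 20 per group. If 30% is the control rate and a reduction is sought, the matching figure is about 75% (exact 78%), and the protocol understates its power by about 18 points. On both readings the figure does not describe the number of days that 10.8 and the SAP analyse.

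This rests on three readings: 20 patients per group, equal groups, and a difference in percentage points. Together they return the plan's own figure, but the plan does not spell them out. That a fall is the target is inferred from the interventions.

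The consequence is small, since the comparison is exploratory. Correction is still worthwhile, because the statement appears twice and cannot be interpreted as written.

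**What to change.** In Protocol 10.8 and the synopsis, if the power sentence is kept:

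- State both assumed diarrhea rates and which sub-cohort is the control.
- State that 20 is the number per group, if that is meant.
- State that the quantity is a proportion, and of what.
- Give about 75% if 30% v 5% is meant, or keep 57% if 30% v 55% is meant. The sponsor has to say which; the documents do not settle it.
- Remove the power claim for number of days, and present days of diarrhea descriptively, as the SAP already does.

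Deleting the diarrhea power claim altogether would also do. Either way the cost is wording in two places, with no change to design, data collection or analysis.

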**Table 2 Disease Control Rate – Third Line** 

	Monotherapy (Historical)	Combination * (Historical)	Combination with BBI608 (Expected)
Cetuximab	30-40% 	~ 63% 	60% or more
Panitumumab	30-40% 	~ 68% 	60% or more
Capecitabine	~ 15% 	~ 45% 	60% or more

\* Cetuximab + Irinotecan
Panitumumab + Irinotecan
Capecitabine + Mitomycin C

For the Cetuximab and Panitumumab combination cohorts, if the disease control rate in stage 1 reaches 3 of 8 or above, additional patients will be enrolled into the stage 2 cohort. For the

Capecitabine combination cohort, if the disease control rate in stage 1 reaches 2 of 6 or above, additional patients will be enrolled into the stage 2 cohort.

To evaluate the tolerability of BBI608, patients from each arm will be assigned to one of 4 subcohorts (with 6 patients in each sub-cohort IA, IB, IIA, IIB). The evaluation of tolerability will be done at select centers for the study arm that is continuing patient accrual and in which a total of 50 evaluable patients has not been reached. For each combination arm, patients assigned to sub-cohorts IA and IB will receive BBI608 at 240 mg po twice daily (480 mg total daily dose) starting on day 1 of cycle 1. Intra-patient dose escalation of BBI608 to 480 mg po twice daily (960 mg total daily dose) is allowed as tolerated. Patients assigned to sub-cohorts IIA and IIB will receive BBI608 at 480 mg po twice daily (960 mg total daily dose) starting on day 1 of cycle 1. In case of toxicity, dose adjustment of BBI608 is permitted, as recommended in dose modification guidelines. Additionally, patients assigned to sub-cohorts IA and IIA will receive prophylactic anti-diarrheal treatment starting the day prior to day 1 of cycle 1. Patients assigned to sub-cohorts IB and IIB will anti-diarrheal treatment on an as needed basis starting with development of diarrhea above baseline. For each combination regimen, patients will be sequentially assigned to each of the 4 sub-cohorts in the following order until 6 patients are accrued on each of the sub-cohorts: IA, IB, IIA, and IIB. If required, up to additional 20 patients may be assigned to selected sub-cohorts to validate the observations in initial 6 patients.

Table 3 Tolerability Analysis of BBI6	U8
---------------------------------------	----

Sub-cohort	BBI608 Starting Dose Level	Anti-diarrheal Administration

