## 7.4 Blinding

This is an open label study. Neither the patient nor the investigator and site staff will be blinded to the treatment administered.

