### 11.2 Registration and Enrollment

This is an open-label, non-randomized study. Boston Biomedical should be notified as soon as a subject qualifies for entry in the protocol. Subjects will be registered by faxing Boston Biomedical or their designee, within 7 days prior to the 1st drug administration. At that time the combination arm will be assigned. The subject will be enrolled into the study when the subject receives the 1st dose of study drug. Registration and enrollment forms and faxing instructions will be provided with the case report forms (CRFs). The site should maintain a log of all subjects who are screened but do not qualify for the study or who do not receive study drug. The reason for disqualification should be noted in the log.

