combination arm, patients assigned to sub-cohorts IA and IB would receive napabucasin at 240 mg twice daily (480 mg total daily dose) starting on Day 1 of Cycle 1. Intra-patient dose escalation of napabucasin to 480 mg twice daily (960 mg total daily dose) was allowed for patients in these cohorts as tolerated. Patients assigned to sub-cohorts IIA and IIB would receive napabucasin at 480 mg twice daily (960 mg total daily dose) starting on Day 1 of Cycle 1. In the event of toxicity, dose adjustment of napabucasin was permitted, as recommended in dose modification guidelines. Additionally, patients assigned to sub-cohorts IA and IIA would receive prophylactic anti-diarrheal treatment starting the day prior to Day 1 of Cycle 1. Patients assigned to sub-cohorts IB and IIB would receive anti-diarrheal treatment on an as-needed basis starting with development of diarrhea (ie, any occurrence greater than the patient's baseline). For each combination regimen, patients would be sequentially assigned to each of the 4 sub-cohorts in the following order until 6 patients were accrued in each of the sub-cohorts: IA, IB, IIA, and IIB. If required, up to an additional 20 patients might be assigned to selected sub-cohorts to validate the observations in the initial 6 patients.

Sub-cohort	Napabucasin Starting Dose Level	Anti-diarrheal Administration*
IA	240 mg bid (480 total daily dose) ¹	Prophylactic
IB	240 mg bid (480 total daily dose) ¹	As needed
IIA	480 mg bid (960 total daily dose) ²	Prophylactic
IIB	480 mg bid (960 total daily dose) ²	As needed

Table 1 Tolerability Analysis of Napabucasin

¹Intra-patient dose escalation of napabucasin to 480 mg po twice daily (960 mg total daily dose) is allowed as tolerated. ²In case of toxicity, dose adjustment of napabucasin is permitted.

*See protocol amendment 2 [5] section 7.1.4 for details

A study cycle would consist of 28 days of daily administration of napabucasin in combination with cetuximab or panitumumab, or capecitabine. Cycles would continue until unacceptable toxicity, disease progression (clinical or radiological) or another discontinuation criterion is met. Pharmacokinetic (PK) assessments would be performed on the first 6 patients enrolled in each combination arm. Pharmacodynamic assessments would be performed in patients with readily accessible tumor tissue through an optional tumor biopsy. Evaluation of anti-tumor activity would be performed at 8-week intervals per RECIST 1.1 while patients remain on study.

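### Protocol 10.8 says sequential allocation by the Sponsor avoids selection bias, but the order is fixed, published and unconcealed, so it removes only the investigator's direct choice of sub-cohort

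*Protocol*

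**What the plan says.** - **The claim.** Protocol 10.8 states: "The patients will be sequentially allocated to different sub-cohorts by the Sponsor to avoid section bias". The synopsis carries the same sentence. The word printed before bias is evidently a slip for selection.
- **The order.** Protocol 4.1 and the synopsis assign patients, within each combination regimen, "in the following order until 6 patients are accrued on each of the sub-cohorts: IA, IB, IIA, and IIB". SAP 2.1 repeats it ("sequentially assigned to each of the 4 sub-cohorts in the following order until 6 patients were accrued in each of the sub-cohorts") and names the same order. The SAP does not repeat the claim about bias.
- **Blinding.** Protocol 7.4: "Neither the patient nor the investigator and site staff will be blinded to the treatment administered".
- **Randomisation and registration.** Protocol 11.2: "This is an open-label, non-randomized study". Patients are registered with the Sponsor before the first dose, and "At that time the combination arm will be assigned". That section does not say how or when the sub-cohort is assigned, or whether the assignment is hidden from anyone beforehand.
- **Use of the sub-cohorts.** Protocol 2.2 has two secondary objectives that compare them: starting dose (240 mg against 480 mg twice daily) and anti-diarrheal strategy (prophylactic against as needed). Protocol 10.8 calls these questions exploratory. It leaves the extension of selected sub-cohorts, by up to 20 patients, to clinical assessment without a formal test.

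**The concern.** Allocation guards against selection bias when the person deciding whether and when to register a patient cannot foresee the assignment. A fixed, published order does not have that property. In an open-label study each assignment is known once made, so the next one follows for anyone who has kept count.

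Two things are at stake. The first is the pair of secondary-objective comparisons, which could partly reflect who was placed in each slot rather than starting dose or anti-diarrheal strategy. The second is the extension decision. It rests on groups of 6, where a few steered patients would matter, and it is made by judgement. A reader of the study report who took 10.8 at its word would believe that both were protected.

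**Working it through.** The plan gives no figure for this point, so there is none to reproduce. The check covers how predictable the next slot is, and what steering could do under stated assumptions.

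**1. Predictability under the published order.** Inputs from Protocol 4.1: 4 sub-cohorts of 6, so 4 × 6 = 24 patients per combination arm, in a fixed order.

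- Someone who knows the running count in the arm predicts 24 of 24 assignments (100%). The Sponsor always knows it.
- The text fits two ways of filling. If sub-cohorts fill one after another, there are 23 transitions and 3 changes of sub-cohort. Guessing that the next patient goes where the last one went is right in 20/23 = 87%.
- If patients rotate IA, IB, IIA, IIB, knowing the last assignment in that arm gives the next one every time.
- Only filling one after another also ties sub-cohort to calendar time. Rotation largely removes that.

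**2. Predictability under random lists.** The guesser knows all earlier assignments and always makes the best guess.

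| Scheme, 24 patients, 4 groups | Share guessed correctly |
|---|---|
| Published fixed order | 100% |
| Random blocks of 4 | 52% |
| Random blocks of 8 | 47% |
| One random block of 24 | 39% |
| Simple randomisation | 25% |

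For blocks of 4 the value is exact: (1/4 + 1/3 + 1/2 + 1)/4 = 0.52. The values for blocks of 8 and 24 come from 20,000 simulated lists each.

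**3. Possible size for the starting-dose contrast.** None of these inputs is in the documents. Assume a share *f* of candidates is frail, their compliance is *d* points lower, and a site that knows the slot picks one of two candidates. It puts a frail patient into a 240 mg slot when it can, and into a 480 mg slot only when both candidates are frail.

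- Frail share in 240 mg slots: 1 − (1 − *f*)²
- Frail share in 480 mg slots: *f*²
- Spurious compliance difference: *d* × [1 − (1 − *f*)² − *f*²] = *d* × 2*f*(1 − *f*)

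Results:

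- *f* = 20%, *d* = 10 points: 10 × (0.36 − 0.04) = 3.2 points.
- *f* = 30%, *d* = 30 points (50% against 80%): 30 × (0.51 − 0.09) = 12.6 points.
- The second case with only half the slots steered and the rest filled at random: 12.6/2 = 6.3 points.
- One candidate per slot, so no choice: 0 points.

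For scale only, Protocol 10.8 uses a 20-point compliance difference in its power statement.

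**4. Anti-diarrheal contrast under the same steering.** Prophylactic treatment is IA and IIA; as-needed treatment is IB and IIB. Each side has one 240 mg and one 480 mg sub-cohort. With *f* = 30% the frail share is (0.51 + 0.09)/2 = 0.30 on both sides, so the spurious difference is 0.

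**The case against.** The other side has several good points.

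- **Sponsor allocation does something.** An investigator cannot directly place a given patient in a given sub-cohort. A reader might infer that there is no protection at all; the documents do not support that. The protection is partial.
- **Site knowledge is not shown.** A reader might infer that sites can work out the next slot. The count runs per combination arm across chosen centres in a multi-center study, and nothing says that sites are told it. Predictability at a single site may be well below 100%. What stands is that no measure is described to hide the count.
- **Calendar-time confounding is conditional.** It follows only if sub-cohorts fill one after another, and the wording also allows rotation.
- **The magnitude is assumed.** The 12.6-point figure needs two eligible candidates at every slot, correct prediction and consistent steering. It should not be read as the expected bias.
- **The comparison is exploratory.** SAP 4.1 plans no hypothesis testing, so no formal error rate is at risk. This limits what may be concluded, but it does not make the statement in 10.8 true, and the extension decision still rests on these patients.
- **Part of the remedy is already planned.** SAP 8.2 summarises data by arm and sub-cohort in general, and SAP 8.2.1 tabulates baseline characteristics.
- **Randomisation is not free and may be too late.** It would change a protocol that describes itself as non-randomised. SAP 4.2.2 speaks of study conduct in the past tense, which suggests that many patients may already have been assigned.

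**Conclusion.** The statement in Protocol 10.8 is wrong as written. Allocation in a fixed, published order, in an open-label and non-randomised study with no concealment described, does not avoid selection bias. It removes only the investigator's direct choice of sub-cohort. Whoever knows the running count in an arm can predict the next slot and could influence whom or when to register.

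The consequence is confined to the exploratory tolerability comparisons under the secondary objectives and to the decision to extend sub-cohorts. A reader might carry it over to the primary endpoint. The documents do not support that: SAP 8.2.2 reports DCR by arm and sub-cohort with exact intervals and compares nothing between sub-cohorts.

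The documents do not fix a size. Under the assumptions shown, the starting-dose contrast could be off by about 3 to 13 compliance points, or by 0 where a site has no choice of candidate. The same steering leaves the anti-diarrheal contrast unbiased. Confounding with calendar time is a possibility that depends on how the sub-cohorts are filled.

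**What to change.** **Patients not yet assigned.** Replace the fixed order with a concealed random list, held centrally by the Sponsor within each combination arm and applied at the registration step in Protocol 11.2. Use large or varying blocks, for example one block of 24, because blocks of 4 remain about 52% guessable in an open-label study. The documents give no safety reason for the fixed order. The cost is the list itself and a protocol amendment with IRB approval (Protocol 12.2 and 13.1), including a change to the wording of 11.2. No extra patients or visits are needed.

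**Patients already assigned in fixed order.** Delete the closing clause on bias from Protocol 10.8 and the synopsis. State in the SAP and the study report that the sub-cohort comparisons are non-randomised and open to selection bias and, if sub-cohorts were filled one after another, to time trends. Say which way of filling was used and what sites were told of the count. Read the comparisons alongside the baseline tables by sub-cohort that SAP 8.2 and 8.2.1 already provide for. This costs a few sentences.
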